#### 3) Need for protocol revision

Discussions will be conducted by appropriate means, such as convening committee meetings, sending internal memos, and hearing opinions by means such as phone, fax, and e-mail.

# 10. Reporting Adverse Events

# 10.1 Definitions of Adverse Events, Serious Adverse Events, Malfunctions, Diseases, and Related Terms

#### 10.1.1 Adverse events

An adverse event is any unfavorable or unintended sign (including abnormal laboratory values), symptom, or disease that occurs during the research period, whether or not it is considered related to the protocol treatment. In this research, an adverse event is defined as any of the above signs, symptoms, or diseases that a subinvestigator considers to be clinically problematic.

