# 9. Definition of Efficacy and Safety Evaluations and Endpoints

# 9.1 Primary Endpoint

Safety will be evaluated by collecting adverse event data.

Evaluation period: From the day of iCEPS transplantation (during transplantation) to Week 52 after iCEPS transplantation or the date of discontinuation

Recording method: The subinvestigator acting as the subject's physician will record the details of each adverse event in the CRF (see "10.4 Response and Follow-up Investigation After Occurrence of Adverse Events"). The subinvestigator and physician-evaluator will make determinations regarding rejection and uncontrollable rejection.

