#### [Rationale for setting]

The endpoint was set to evaluate the safety of the protocol treatment by assessing the overall incidence of adverse events.

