# 9.3 Decision Items for Individual Endpoints

Subinvestigators and physician-evaluators will make determinations regarding decision items for the endpoints specified in "9.1 Primary Endpoint" and "9.2 Secondary Endpoints" at each evaluation time point. The final determination will be made by consensus.

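### Section 10.1.1 narrows adverse events to what a subinvestigator finds clinically problematic, so the 13.2.3 tables can understate the overall incidence that 9.1 sets out to assess

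*Combined protocol and SAP*

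**What the plan says.** - **Definition (protocol 10.1.1).** The first sentence is broad: "An adverse event is any unfavorable or unintended sign (including abnormal laboratory values), symptom, or disease that occurs during the research period", whether or not related to treatment. The second applies to this study and is therefore the operative one: "an adverse event is defined as any of the above signs, symptoms, or diseases that a subinvestigator considers to be clinically problematic".
- **Primary endpoint (9.1).** "Safety will be evaluated by collecting adverse event data". The rationale beneath it says that the endpoint was set "to evaluate the safety of the protocol treatment by assessing the overall incidence of adverse events".
- **Who decides.** "The subinvestigator acting as the subject's physician will record the details of each adverse event in the CRF". The same section brings in a second person for one topic: "The subinvestigator and physician-evaluator will make determinations regarding rejection and uncontrollable rejection". Section 9.3 adds a consensus rule for decision items under 9.1 and 9.2, without listing those items.
- **Analysis (13.2.3).** AEs for which data were collected are listed per subject, and subjects and events are counted per AE. Serious AEs are tabulated similarly. Rejection and neoplastic lesion status are listed at each time point as a separate item.
- **Supplement, section 15 (Outcome evaluation).** It describes the safety assessment as resting on collection of all adverse events.

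**The concern.** A clinical-significance test is ordinary for laboratory values, because many out-of-range results mean nothing. Here the test also governs symptoms and diseases, and the plan does not say what makes a finding problematic. Whether something becomes an AE then depends on the opinion of a subinvestigator in an open-label study without a control group (2.5).

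The AE record is the primary endpoint, so a judgment at the point of entry acts on the main result itself. With four subjects (section 7), one or two unrecorded events visibly change a table, and there is no comparison arm in which the same loss would occur. Section 2.4 says that later trials will build on these safety findings, so a reader needs to know which definition lies behind the counts.

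**Working it through.** **No AE rate to reproduce.** The plan states no expected AE rate. Its only relevant number is the sample size. Section 7 derives recruitment as 100 patients × 10% eligible × 20% enrolling = 2 per year. This gives 4 subjects if accrual lasts two years, a duration that section 7 does not state. The AE definition does not enter that calculation, and changing it leaves n = 4.

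**Direction.** Events that pass the second sentence of 10.1.1 are a subset of those that meet the first. For every AE, the 13.2.3 count is therefore at most the count under the broad definition. This needs no assumption.

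**Serious events.** Section 10.1.2 defines a serious AE as an AE that meets one of six criteria, so the test formally sits upstream of seriousness too.

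**Which expected events have a route around the test?** Section 10.7.1 lists 11 expected surgical events.
- Four are graded under 9.2 whether or not anyone calls them an AE: the six subjective symptoms, corneal epithelial defect, symblepharon, and conjunctivalization (through LSCD stage).
- The other 11 − 4 = 7 have no scale in 9.2: conjunctival hyperemia, superficial punctate keratopathy, infectious keratitis, raised intraocular pressure, cataract, corneal keratinization and endophthalmitis. Some of these would hardly be judged unproblematic. Hyperemia and punctate keratopathy easily could be.
- The post-transplantation gradings fall at Weeks 2, 4, 8, 16, 24, 32, 40 and 52. The longest gap is 52 − 40 = 12 weeks. An event that comes and goes between visits, or a systemic complaint, has no scheduled grading.

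**Is the entry decision checked?** Section 9.1 names the physician-evaluator only for rejection. Section 9.3 does not say that qualifying as an AE is a decision item. Section 12.4 lets the CRF entry itself be the source document for AE status and details. Nothing requires a log of findings judged not problematic.

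**Illustration only.** Let p be the true per-subject risk of an event and s the share of affected subjects whose event passes the test. The documents give neither, so both are assumptions. With independent subjects, the chance that the event appears in at least one of four is 1 − (1 − p·s)^4.

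| s | p = 0.25 | p = 0.50 |
|---|---|---|
| 1 (no filter) | 68.4% | 93.8% |
| 0.9 | 63.9% | 90.8% |
| 0.75 | 56.4% | 84.7% |
| 0.5 | 41.4% | 68.4% |
| 0.25 | 22.8% | 41.4% |

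Worked example for p = 0.25, s = 0.5: 1 − (1 − 0.125)^4 = 1 − 0.586 = 41.4%. The table shows only how sensitive a four-subject record is to the unknown s.

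**The case against.** The strongest reply is that the plan collects far more safety information than the AE form. The six symptoms are graded 0 to 4, and LSCD stage, epithelial defect and symblepharon are determined by consensus with a physician-evaluator. Slit-lamp examination with photography is scheduled with safety as a stated purpose (8.2). Laboratory values are scheduled (8.7), concomitant drugs go into the CRF (6.3), and medical records are open to monitors and auditors (19, 20.1). Malfunctions (10.1.3) and diseases suspected to be caused by the product (10.1.4) carry no clinical-problem test. Section 10.2 grades easily bearable eye events as mild, so the plan evidently expects minor events to be recorded.

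Most of this stands, and it rules out three stronger readings that a reader might infer:
- That events judged unproblematic leave no trace and cannot be recovered. Graded symptoms and signs, images, laboratory results and medical records contradict this for much of the list, including discomfort.
- That the primary analysis contains only filtered events. Rejection and neoplastic lesion status, central risks of this product, are listed at each time point.
- That the endpoint cannot deliver an overall incidence. It can deliver the incidence of AEs as the plan defines them. What it may miss is incidence under the first sentence of 10.1.1.

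The reply does not close the gap. Information held in gradings, images or charts does not enter the 13.2.3 AE counts unless someone decides that it is an AE. Sections 10.1.3 and 10.1.4 feed the reporting duties in 10.5 and 10.6, not those tables. Section 10.2 shows that mild events are meant to count, but does not say when an easily bearable sign becomes problematic.

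A second objection concerns the remedy and is accepted. LSCD itself causes pain, dryness and similar complaints (2.4), so simply deleting the second sentence could turn stable disease into AEs. A baseline rule is needed.

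**Conclusion.** The point holds as an unreconciled double definition that can lower the primary-endpoint counts. The direction follows from the text. The size cannot be estimated: the documents give neither AE rates nor the share of findings that would be judged unproblematic, and any percentage for under-recording would be pure assumption. The practical exposure is mainly to ungraded signs such as hyperemia and punctate keratopathy, to events between visits and to systemic events. For serious AEs the exposure is formal. Few events meeting 10.1.2 would plausibly be judged unproblematic, though that is a judgment and not something the plan secures.

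This is a flaw of definition and ascertainment, not a numerical error, and it does not invalidate the study. The documents do not show that any event was in fact left out. The plan should be changed because the affected record is the primary endpoint and the repair is small.

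**What to change.** 1. In 10.1.1, limit the clinical-problem test to abnormal laboratory values.
2. Record as an AE every other unfavorable sign, symptom or disease that is new or worse than the pre-transplantation baseline. Section 13.2.4 already defines baseline as the day of transplantation, before surgery. Stable LSCD symptoms are then not counted.
3. Keep the subinvestigator's judgment as a yes/no CRF field and show it in the 13.2.3 listing, so that both the full and the narrower counts can be tabulated.
4. For data already collected, state in the study report which definition was applied, and cross-check the AE listing against the visit gradings and medical records. Reconcile the supplement's statement about collecting all adverse events with the result.

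The cost is one revised sentence, one CRF field and somewhat longer listings. The retrospective check covers four subjects. It can recover only what was written down or imaged, so events between visits that were never charted stay unknown.

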#### 10.1.2 Serious adverse events

A serious adverse event is any adverse event that:

- 1) results in death;
- 2) is life-threatening;

The term "life-threatening" here refers to an event in which the subject was at risk of death at the time of the event; it does not refer to an event that hypothetically might have caused death if it were more severe.

- 3) requires hospitalization or results in prolongation of existing hospitalization;
- 4) results in persistent or significant disability/incapacity;
- 5) is a congenital anomaly/birth defect; or
- 6) is a medically important event.

The term "a medically important event" here refers to an important medical event that might not be immediately life-threatening or result in death or hospitalization but might jeopardize the subject or might require intervention to prevent one of the other outcomes listed in the aforementioned definition.

#### 10.1.3 Malfunctions

A malfunction is any issue with the function of the specific processed cell product or adverse effect of the cells on the human body, by a broad scope of definition, regardless of the stage in which it arose, whether it was during production, supply, storage, or use.

#### 10.1.4 Diseases or the like

"Diseases or the like" indicates disease, disability, death, or infectious disease that is suspected to be caused by provision of the regenerative medicine product as described in the regenerative medicine provision plan.

#### 10.2 Assessment of Adverse Events

The severity of adverse events will be determined using the JCOG Japanese translation of the Common Terminology Criteria for Adverse Events v4.0 (CTCAE v4.0 - JCOG). However, adverse events localized to the eye will be classified into three levels of severity (mild, moderate, or severe) as follows:

Severity assessment of adverse events localized to the eye:

Mild : Signs or symptoms that are easily bearable,

Moderate: Signs or symptoms that interfere with daily activities, or Severe: Signs or symptoms that hinder work or daily activities.

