# 3.2 Eligibility Criteria

Patients who meet all of the inclusion criteria and none of the exclusion criteria are eligible for the research.

[figure not shown]
iCEPS will be transplanted only in one eye. If both eyes meet the transplantation criteria, the transplantation approach will be determined comprehensively by referring to the following items and consulting with the patient:

- Visual acuity
- · Corneal stromal opacity
- Cataract
- Tear fluid volume, etc.

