# 10.7 Expected Adverse Events

# 10.7.1 Adverse events caused by transplantation surgery/procedures

1) Conjunctival hyperemia

Treatment: Topical or systemic anti-inflammatory agents

2) Subjective symptoms (eye pain, foreign body sensation, lacrimation, photophobia, dryness, and discomfort)

Treatment: Eye drops, eye ointment, or oral medication for serious cases

3) Superficial punctate keratopathy

Treatment: Eye drops or eye ointment administered locally for serious cases

4) Corneal epithelial defect

Treatment: Eye drops or eye ointment for serious cases

5) Symblepharon

Treatment: Surgical release of adhesions for serious cases

6) Conjunctivalization

Treatment: Eye drops or eye ointment as needed for serious cases

7) Infectious keratitis

Treatment: Antibiotics, antivirals, or antifungals, and surgical treatment as needed

8) Increased intraocular pressure

Treatment: Local or systemic antiglaucoma agents, and surgical treatment as needed

9) Cataract

Treatment: Surgical treatment for serious cases

10) Corneal keratinization

Treatment: Removal of corneal keratinization for serious cases

11) Endophthalmitis

Treatment: Antibiotics, antivirals, or antifungals, and surgical treatment as needed

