#### 13.2.3 Primary endpoint (safety)

Adverse events for which data were collected will be listed for each subject (event name, onset date, outcome date, duration, outcome, severity, seriousness, causal relationship with the protocol treatment, and rationale for causality determination). The number of subjects who experienced the event and the number of events will also be shown for each adverse event. Duration is defined as "outcome date – onset date + 1 (day)." Serious adverse events will be tabulated in a similar fashion.

Neoplastic lesion status and rejection status at each time point will also be listed, along with details of relevant laboratory results.

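### The ocular severity scale does not separate moderate from severe and leaves one kind of event ungraded, so the moderate/severe split in the primary safety listing is not reproducible

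*Combined protocol and SAP*

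**What the plan says.** The primary endpoint is safety: "Safety will be evaluated by collecting adverse event data" (protocol 9.1). Section 13.2.3 lists each adverse event by subject, with fields that include "event name, onset date, outcome date, duration, outcome, severity, seriousness". Severity and seriousness are therefore two separate columns.

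Section 10.2 grades adverse events by CTCAE v4.0 in general but makes an exception: "adverse events localized to the eye will be classified into three levels of severity (mild, moderate, or severe"). Mild is "Signs or symptoms that are easily bearable". The other two levels are: "Moderate: Signs or symptoms that interfere with daily activities, or Severe: Signs or symptoms that hinder work or daily activities". No level refers to visual acuity, to a clinical sign or to the need for treatment. Nothing says which level applies when an event meets more than one.

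Section 10.7.1 lists the events expected from surgery. One of them is "Increased intraocular pressure".

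**The concern.** A severity scale should put each event in one level and only one. Here the test for moderate is contained in the test for severe, and the two differ only by near-synonymous verbs and the added word *work*. Two raters who follow the protocol could give the same event different grades, and neither would be wrong.

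The study is open-label and uncontrolled, has four subjects and is purely descriptive (2.5, 7, 13.3). The safety conclusion therefore comes from reading the listings. For eye events, the severity column of those listings depends on this scale and not on CTCAE.

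The scale also measures only how bearable an event is and what it does to function. It does not say how to grade a sign that the patient does not feel.

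**Working it through.** No sample size, error rate or event count is involved, so there is no figure of the plan to reproduce. The check is a truth table on the definitions in 10.2.

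**Inputs.** Three yes/no attributes taken from the wording: easily bearable (B), affects daily activities (D), affects work (W).

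**Rules as written.** Mild if B. Moderate if D. Severe if D or W. *Interfere with* and *hinder* are read as the same degree, because the text gives no threshold between them.

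| B | D | W | Levels met |
|---|---|---|---|
| yes | yes | yes | mild, moderate, severe |
| yes | yes | no | mild, moderate, severe |
| yes | no | yes | mild, severe |
| yes | no | no | mild |
| no | yes | yes | moderate, severe |
| no | yes | no | moderate, severe |
| no | no | yes | severe |
| no | no | no | none |

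**Results.**

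- All 4 combinations that affect daily activities meet both moderate and severe. None of the 8 meets moderate without severe.
- The 2 combinations that affect work but not daily activities meet severe and not moderate. The definitions are therefore nested, not identical.
- One combination (not easily bearable, no limit on work or daily activities) meets no level.
- A sign with no symptoms and no functional effect falls in the fourth row and can only be mild.

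These are counts of logical combinations, not of events. Combinations that are easily bearable and yet limit function may be rare. Without those three rows, 5 remain: 2 have a single level, 2 meet both moderate and severe, and 1 has no level.

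**Two other readings.** If the highest level met is assigned, a convention that 10.2 does not state, the moderate level is empty. If *hinder* is meant as a stronger degree than *interfere with*, moderate does have cases of its own. The cut-point between the two is still undefined, and the last row still has no level.

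**Check of the proposed levels.** Take bearability (2 states) by effect on usual activities including work (none, interferes, prevents): 2 × 3 = 6 combinations. Mild is easily bearable with no effect (1). Moderate is not easily bearable, or interferes, but does not prevent (3). Severe is prevents (2). 1 + 3 + 2 = 6, so each combination has exactly one level.

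**The case against.** The strongest reply is that an ordered list of mild, moderate and severe signals that *hinder* is the higher degree, and that the distinction may have been lost in translation. The revision history does mention a corrected mistranslation in another section. This is plausible, but the documents cannot settle it, and the English text still gives no boundary.

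A second reply is that section 9.3 has subinvestigators and physician-evaluators decide by consensus, and that the listing gives the name, dates, outcome, seriousness and causality of every event. With four subjects, a reader can see what each event was. That limits the harm. But consensus settles who decides, not what the levels mean, so the grade still cannot be checked against its definition.

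Several stronger readings are tempting, and the documents do not support them:

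- *The two levels are the same test, so every non-mild ocular event is ambiguous.* Severe adds work, and an event that affects work alone is severe only.
- *Silent sight-threatening events escape the safety record.* Section 10.1.2 counts medically important events and significant disability as serious, whatever the severity grade. Section 10.6 sets 15-day reporting for suspected product-related conditions that carry a risk of disability. LSCD stage, epithelial defect, opacification, neovascularisation and symblepharon have their own anatomical grades (9.2), and rejection and neoplastic status are listed at each time point (13.2.3). Pressure has no grade of its own in 9.2, so for that sign the seriousness column is the safeguard.
- *The untreated eye will keep daily function intact and hide damage.* The plan does say "iCEPS will be transplanted only in one eye", but section 3.2 also provides for patients whose two eyes both qualify, and it says nothing about function in the fellow eye.
- *A stated share of the expected events in 10.7.1 is silent, or most events will be ocular.* The plan gives no basis for either. Section 2.4 describes conjunctivalisation as causing symptoms and visual impairment, and the systemic corticosteroids and cyclosporine in 6.2 make systemic events plausible too.

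**Conclusion.** The concern holds as a defect in a stated rule. On its wording, the ocular scale in 10.2 is neither exclusive (every moderate event is also severe) nor exhaustive (one combination has no level). The moderate/severe split in the severity column of 13.2.3 is therefore not reproducible, and a claim that no ocular event was severe cannot be verified against the definitions. A symptomless sign cannot be graded above mild, and that limit applies to the severity column alone.

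The size is modest. Severity is one descriptive column for four subjects. No test uses it (13.3), the midterm decision rests on rejection findings (9.4), and the criteria for stopping the whole study name no severity grade (11.1). The plan gives no number of ocular events by grade, so the number affected cannot be stated.

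The conclusion assumes that the two verbs carry no defined difference of degree, which is what the English text shows. A clear distinction in the original language would remove the overlap if carried into the English text. It would not by itself fill the gap or settle the grading of symptomless signs. The documents do not support a reader's inference that the safety conclusion as a whole is unsound.

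**What to change.** 1. Check the original-language wording of 10.2. If it separates the levels, correct the English text.
2. Make the levels mutually exclusive and exhaustive. For example: mild = easily bearable with no effect on usual activities; moderate = not easily bearable, or interferes with but does not prevent usual activities, including work; severe = prevents work or usual daily activities.
3. State how symptomless ocular signs are graded, and that their severity is to be read together with the seriousness column. A 'threatens vision' clause should not be added to severe: it would mix seriousness, which 10.1.2 already covers, into severity.
4. Regrade the ocular events of the four patients by the consensus process in 9.3. The supplement (section 15) already reports events to week 104, so data may be locked. If so, show the regrade beside the original grade, and follow 13.5 by revising the protocol and explaining the change in the clinical study report.

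The cost is a few lines in 10.2 and a small regrading exercise. Some events may change grade in either direction. For example, an event that hampers work without preventing it can be severe on the present wording and would become moderate. That is a further reason to show both grades.
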